We expect that this parent-based behavioural sleep intervention will improve the sleep quality of children with ADHD, which in turn may lower inattention/hyperactivity impairment, reduce parental stress and improve the child's daily functioning.

Objectives and Hypothesis of the study

To assess the effect of a brief parent-based sleep behavioural intervention on the sleep quality as well as other aspects of functioning and mental health of children with ADHD and their parents.

Compared to children with ADHD and insomnia receiving treatment as usual, the group of children with ADHD and insomnia receiving the parent-based intervention will have better sleep and functioning as well as parental mental health at post-intervention and follow-up at 3 months.

Study Design/Methodology

Study Sites

Alice Ho Miu Ling Nethersole Hospital, TaiPo, N.T., Hong Kong

Sleep Research Clinic & Laboratory, Department of Psychology, The University of Hong Kong

Study Population

Parents of children who meet all the following inclusion criteria and none of the exclusion criteria will be our target participants.

Inclusion criteria:

ADHD with sleep problem(s)

- Aged 6-12 years old;
- With a clinical diagnosis of ADHD (any subtype), as confirmed by the Diagnostic Interview Schedule for Children-version-IV (DISC-IV);
- With parent-reported insomnia (difficulty initiating sleep and/or maintaining sleep).

Exclusion criteria:

1. Children with a serious medical condition (e.g. severe cerebral palsy) or intellectual disability (IQ<70);
2. Children with a neurological and/or medical condition that may lead to disordered sleep;
3. Suspected clinical sleep disorders (e.g. obstructive sleep apnea, OSA) that may potentially contribute to a disruption in sleep continuity and quality, as assessed by the Children's Sleep Habits Questionnaire (CSHQ). If the child is suspected of a clinical sleep disorder, he/she will be

referred to appropriate services;

4. Children who are already receiving specialized help for their sleep from a psychologist or at a specialized sleep clinic.

A total of 60 families will be invited to participate in this programme and will be randomized into intervention group and waitlist-control group (30 families each).

Subject Recruitment Plans and Consent Process

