Demographics & health history. Each family will complete a brief questionnaire so as to provide sample characteristics of the child (demography, family characteristics, medical history). Prescribed medication(s) of the child at the time of study will be documented and recorded.

Evaluation survey. Each family will be invited to complete a brief evaluation survey to provide feedback on the usefulness and arrangement of the intervention.

Measures on sleep, ADHD symptoms, other clinical symptoms and functioning, and cognitive performance of the child, as well as parental sleep and mental health will be administered at the following time-points for the intervention and waitlist-control group: before the intervention programme (baseline); after the intervention (one-week after the follow-up call to assess the short-term effects of the intervention). The above measurements will be additionally conducted for the intervention group at 3 months after the intervention to assess any long-term effects of the treatment.

Statistical Analysis Plan

Sample Size Determination and Power

The primary outcome is the child's sleep based on parental report (e.g. CSHQ, sleep problems rated by parents), as a measure of intervention efficacy. Secondary outcomes include other sleep measures (e.g. actigraphic parameters, daytime sleepiness), daytime functioning, quality of life and other

clinical symptoms and behavior of the child, as well as parental sleep and mental health. A previous representative study found an effect size of -0.8 for CSHQ at 3 months follow-up, which would require 26 families in each arm to have 80% power at the two-sided 5% level of significance to detect this effect.⁴⁹ To allow for 15% loss to follow-up, we require 30 families in each group.

Analysis Plan

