Preliminary descriptive analysis will be conducted to compare the two groups (intervention, wait-list control) for any baseline differences in sleep and functioning characteristics. Subsequent analysis will be conducted on an intention to treat basis. For child- and parent-related measures, changes between baseline and post-intervention as well as between baseline and follow-up at 3 months will be computed. Mean differences in change at 95% confidence interval in outcomes between intervention and control arms will be estimated with regression models, adjusting for covariates as well as baseline scores for each specific measure if there are any group differences.⁵⁰ Potential covariates to be considered include the child's age, sex, medication use (yes or no), and family socioeconomic status (measured by monthly family income). As for computing effect sizes, changes in each outcome will be standardized to a mean of 0 and standard deviation of 1, before repeating the regression analyses. Effect sizes are interpreted as small, moderate and large for standard deviations of ~0.20, 0.50, and .80 respectively.⁵¹

Declaration of Helsinki

The study will follow the ethical principles under the Declaration of Helsinki. The right of all individuals to self-determination and the right to make informed decisions regarding participation in research, both initially and during the course of the research are respected. Participants' welfare would take precedence over the interests of science and society, and ethical consideration would take precedence over laws and regulations.

Privacy and confidentiality

Participants' names will be kept on a password-protected database and will be linked only with a study identification number for this research. There are no patient identifiers. Data will be stored in a locked office of the investigators and maintained for a minimum of three years after the completion of the study.

Risk/Benefit to participants

This study does not present any risks to the participants. Selected participants will all receive a behavioural sleep intervention and related education materials.

References

1. Clinical practice guidelines: diagnostic and evaluation of the child with attention deficit/hyperactivity disorder. American Academy of Pediatrics Committee on Quality Improvement. *Pediatrics* 2000; 105, 1158-1170.

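### Only the intervention arm is assessed at 3 months, so the 3-month comparison with controls in the hypothesis and Analysis Plan, whose effect size sets the sample size, cannot be made

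*Protocol*

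**What the plan says.** All the relevant text is in the Protocol.

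- **Schedule (Measurements, Other Information).** For both groups, the measures "will be administered at the following time-points for the intervention and waitlist-control group: before the intervention programme (baseline); after the intervention". The second time point is defined as "one-week after the follow-up call to assess the short-term effects of the intervention". The next sentence adds the third, at which the measurements are "additionally conducted for the intervention group at 3 months after the intervention to assess any long-term effects of the treatment".
- **Hypothesis (Objectives and Hypothesis of the study).** Compared with children receiving treatment as usual, the intervention group "will have better sleep and functioning as well as parental mental health at post-intervention and follow-up at 3 months".
- **Analysis Plan.** Changes are computed from baseline to post-intervention and from baseline to 3 months. Then: "Mean differences in change at 95% confidence interval in outcomes between intervention and control arms will be estimated with regression models". That sentence is not limited to one time point.
- **Sample Size Determination and Power.** "A previous representative study found an effect size of -0.8 for CSHQ at 3 months follow-up, which would require 26 families in each arm", with 80% power at the two-sided 5% level. Allowing for 15% loss, this becomes 30 families per group.
- **Risk/Benefit to participants.** "Selected participants will all receive a behavioural sleep intervention and related education materials". The protocol does not say when the waitlist families receive it.

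**The concern.** The first schedule sentence names both groups and the next names only the intervention group, so the 3-month visit excludes controls. Nothing elsewhere in the protocol schedules a control measurement at that time. The hypothesis, and on its natural reading the regression, still call for a comparison with controls there, and the only effect size given comes from that time point.

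A statistical analysis plan cannot repair this. It can choose a model, but it cannot supply observations that are not collected. With no 3-month value from any control family, an imputed control mean would rest on assumption alone.

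Two things are at stake:

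- **Interpretation.** The 3-month result would be an uncontrolled before-after change. Children enter because their parents report insomnia, so some improvement is expected from regression to the mean and natural course. The protocol itself cites a paper on regression to the mean in support of its adjustment for baseline. The repeated computerised tests are also open to practice effects. Without controls none of this can be separated from the treatment effect.
- **Power.** The stated calculation is tied to a time point at which this trial has no comparison. The contrast the trial does have carries no power statement of its own.

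**Working it through.** **1. Who is measured when**

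Session 1 is taken as week 0. The sessions are fortnightly, the call follows two weeks after the second session, and the assessment one week after the call: 0 + 2 + 2 + 1 = week 5.

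| Time point | Intervention | Control | In hypothesis | Change score in Analysis Plan | Source of effect size |
|---|---|---|---|---|---|
| Baseline | yes | yes | – | – | – |
| Post-intervention (about week 5) | yes | yes | yes | yes | no |
| 3 months after the intervention | yes | **no** | yes | yes | **yes** |

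The last row is the contradiction. Scheduled control observations at 3 months: 0, against 26 required.

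**2. Reproducing the protocol's own figure**

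Inputs, from Sample Size Determination and Power: standardised effect d = 0.8, two-sided alpha 0.05, power 80%, equal arms.

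- Normal approximation: n per arm = 2(1.960 + 0.842)² / 0.8² = 24.5, so 25.
- Two-sample t-test (non-central t): n per arm = 25.52, so **26**. This matches the protocol.
- Allowance for 15% loss: 26 × 1.15 = 29.9, so 30; 26 / 0.85 = 30.6, so 31. The one-family difference is immaterial.
- Expected completers from 30 per arm: 30 × 0.85 = 25.5.

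The arithmetic is sound. The difficulty is the time point it refers to.

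**3. Power of the contrast that exists**

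Power = P(|T| > t critical), where T is non-central t with 2n − 2 degrees of freedom and non-centrality d√(n/2). At n = 26 and d = 0.8 the non-centrality is 0.8 × √13 = 2.88 on 50 degrees of freedom, giving 80.7%.

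The protocol gives no post-intervention effect size, so the values of d below are assumptions.

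| Assumed d at post-intervention | Power, 25.5 per arm | Power, 26 per arm | n per arm for 80% |
|---|---|---|---|
| 0.9 | 88% | 89% | 21 |
| 0.8 | 80% | 81% | 26 |
| 0.7 | 69% | 70% | 34 |
| 0.6 | 56% | 56% | 45 |
| 0.5 | 42% | 42% | 64 |

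The smallest effect detectable with 80% power at 26 per arm is 0.79 SD.

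**The case against.** The strongest reply is that the randomised comparison survives. Both arms are measured at post-intervention, the hypothesis names that time point too, and the Analysis Plan lists that change first. A waitlist design with longer follow-up of the treated arm alone is a legitimate choice. This stands: only the 3-month part of the hypothesis and regression fails.

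Second, in the power sentence the 3 months describes the earlier study's result, and the protocol never names its own primary time point. Strictly, it does not claim 80% power at 3 months. This is fair but does not help the plan. If 3 months is primary, the primary comparison does not exist. If post-intervention is primary, the effect has been borrowed from another time point without justification.

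Third, nothing in the protocol says that the short-term effect is smaller than the 3-month one, so the lower powers are illustrative. That is accepted. The effect could also be larger, and the table includes 0.9 for that reason. The firm number is the 0 control observations.

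Fourth, practice effects concern the cognitive tests, which are not among the listed primary and secondary outcomes. That is correct. For parent-reported sleep, the relevant threats are regression to the mean and natural course.

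**Conclusion.** The concern holds and must be fixed. The assessment schedule contradicts the 3-month part of the hypothesis and leaves the 3-month between-arm regression without control data. The sample size rests on an effect from a time point at which this trial has no controls. The post-intervention comparison is intact, but it has at least 80% power with the planned completers only if the effect there is about 0.8 SD, which the protocol does not argue.

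The conclusion about the missing comparison rests on the text alone. The power figures assume a two-sample t-test, equal arms, exactly 15% loss in each arm and no gain in precision from baseline adjustment.

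**What to change.** **Preferred: wording only**

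- Name the post-intervention assessment as the time point of the randomised primary comparison.
- Remove 3 months from the between-arm hypothesis and from the between-arm regression.
- Describe the 3-month data as within-arm, descriptive information on maintenance in the intervention group.
- Restate the power for post-intervention, for example that 26 evaluable families per arm give 80% power to detect 0.79 SD on the CSHQ, and add a reason why an effect of that size is plausible about 5 weeks after the first session. If a smaller effect is more realistic, the table shows the sample size needed.

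The price is a narrower claim about long-term benefit.

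**Alternative: keep the 3-month comparison**

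- Schedule the 3-month assessment in the control arm as well. The required number stays at 26 evaluable per arm.
- State when control families receive the programme and reconcile this with the 3-month assessment. If some have already received it by then, the comparison is no longer with treatment as usual.
- The CSHQ alone would support only the sleep part of the 3-month claim. The hypothesis also covers functioning and parental mental health, so those measures would have to be collected too or the claim cut back.

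The direct cost is one more assessment round in about 30 control families, plus whatever follows from reconciling its timing with their receipt of the programme. The decision is needed before controls pass the 3-month point, because those data cannot be recovered afterwards.

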Child-related Measures

Sleep Problems & Daytime Functioning

Children's Sleep Habits Questionnaire (CSHQ) – parent report.¹⁵ A validated 50-item parent-report measure of difficulties initiating and maintaining sleep over past week in children of age 4-12 (Cronbach's alpha=0.79). Items are rated on a three-point scale from "rarely" to "usually", and scores range from 33 to 99. The validated Chinese version will be used.¹⁶

Pediatric Daytime Sleepiness Scale (PDSS) – parent report. A validated 8-item self-report scale to measure daytime sleepiness in children and adolescents (Cronbach's Alpha=0.80).¹⁷ The Chinese version has been validated.¹⁸

Actigraphy. Assessed with Actiwatch 2 (Philips Respironics, Murrysville, PA), a small motion sensor attached to the non-dominant wrist to measure body movements. Indicators such as total sleep time, sleep onset latency, wake after sleep onset, and sleep efficiency (ratio of time asleep to time spent in bed) will be measured. Movement patterns can then be analysed in terms of sleep and wake times according to established scoring rules.¹⁹

Sleep diaries – parent report. Daily primary caregiver report of child sleep during the two 7-days sessions of actigraph measurement.

ADHD Diagnosis & Symptoms

Diagnostic Interview Schedule for Children – Version-IV (DISC-IV) – parent report. To confirm the diagnosis of attention deficit/hyperactivity disorder (ADHD) based on DSM-IV.²⁰ DISC-IV was validated locally.²¹ Functional impairment scores to achieve a full DSM-IV diagnosis were included, according to published scoring algorithms for the DISC-IV, equivalent to one severe or at least two intermediate impairments in six domains of daily functioning.²²

Strengths and Weaknesses of ADHD Symptoms (SWAN) – parent report. The Chinese version of SWAN rating scale is an 18-item questionnaire for assessment of ADHD symptoms, validated locally for Chinese children in Hong Kong.²³ Parents are asked to compare the child's inattention and hyperactivity behaviours with children of the same age using a 7-point scale. Scores range from -3 (far better than peers) to +3 (far worse than peers), with 0 denoting average behaviour. The total scale score had excellent internal consistency (Cronbach's Alpha=0.90), test-retest reliability, and good discriminant validity in differentiating ADHD clinic sample from community sample.²³

Behaviour, Other Clinical Symptoms & Functioning

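### The primary outcome is given only as examples, with no score or time point, and its power rests on a 3-month effect although only the intervention group is measured at 3 months

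*Protocol*

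**What the plan says.** All references are to the protocol.

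- **Primary outcome** (Sample Size Determination and Power): defined as a domain, namely "sleep based on parental report (e.g. CSHQ, sleep problems rated by parents), as a measure of intervention efficacy". No score is named and no visit is attached.
- **Basis of the sample size** (same section): an earlier study's "effect size of -0.8 for CSHQ at 3 months follow-up", giving 26 families per arm for 80% power at two-sided 5%, raised to 30 for 15% loss.
- **Measurement schedule** (end of Other Information): both groups are assessed at baseline and one week after the follow-up call. Then: "The above measurements will be additionally conducted for the intervention group at 3 months after the intervention". No section schedules a 3-month assessment of the waitlist group.
- **Hypothesis** (Objectives and Hypothesis of the study): compared with usual treatment, the intervention group will have "better sleep and functioning as well as parental mental health at post-intervention and follow-up at 3 months".
- **Analysis Plan**: "changes between baseline and post-intervention as well as between baseline and follow-up at 3 months will be computed". The regression sentence that follows estimates differences in change between the arms.
- **Instruments** (Sleep Problems & Daytime Functioning): for CSHQ, "scores range from 33 to 99". The parent sleep diary is also listed: "Daily primary caregiver report of child sleep during the two 7-days sessions of actigraph measurement".

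**The concern.** There are two linked problems.

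First, a primary outcome introduced by examples does not identify one endpoint. The second example may only restate CSHQ, but the text does not say so. The parent-completed diary also fits the description, and the list of secondary outcomes does not name it. With neither score nor visit fixed, the measure that carries the efficacy claim could be settled after the data are seen. The ratings in question come from parents who know whether they received the intervention.

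Second, the hypothesis and the sample size both point to 3 months, where the schedule provides no control data. A between-arm comparison there cannot be made from the data the protocol collects. The comparison that can be made, at post-intervention, has no effect size of its own, so the protocol's 80% power has not been justified for it.

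**Working it through.** **1. Reproduce the plan's figure.** Inputs from Sample Size Determination and Power: standardised effect d = 0.8, two-sided 5%, 80% power, 1:1 allocation. For a two-sample t-test with n per arm, the noncentrality parameter is d × √(n/2) on 2n − 2 degrees of freedom.

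- Solving for 80% power gives n = 25.5, so 26 per arm, as stated.
- At n = 26: 0.8 × √13 = 2.88 on 50 degrees of freedom, power 80.7%.
- Loss to follow-up: 26 × 1.15 = 29.9, so 30 as stated. Dividing instead gives 26/0.85 = 30.6, so 31. The difference is one family per arm and is not part of this point.

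**2. Set the passages side by side.**

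| Visit | Intervention | Waitlist | Between-arm hypothesis | Source of effect size |
|---|---|---|---|---|
| Baseline | measured | measured | – | – |
| Post-intervention | measured | measured | yes | none given |
| 3 months | measured | not scheduled | yes | -0.8 on CSHQ |

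The visit that supplies the effect size has no controls, and the visit with controls has no effect size. From the described course of treatment (two weeks between sessions, two more to the call, one more to assessment), post-intervention falls about 2 + 2 + 1 = 5 weeks after the first session. The time origin of the earlier study's 3 months is not stated, so the gap between the two visits cannot be computed.

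**3. Power at the one comparable visit.** Keep n = 26 per arm and two-sided 5%. Effects below 0.8 are assumptions; the protocol gives none.

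| Effect at post-intervention | Noncentrality, d × √13 | Power at 26 per arm | n per arm for 80% |
|---|---|---|---|
| 0.8 | 2.88 | 80.7% | 26 |
| 0.7 | 2.52 | 69.7% | 34 |
| 0.6 | 2.16 | 56.4% | 45 |
| 0.5 | 1.80 | 42.4% | 64 |

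**4. False-positive rate if the measure stays open.** With CSHQ alone it is 5%. Suppose instead that two parent-reported measures are each tested at two-sided 5% post-intervention and either may be claimed as primary. The chance of at least one false positive is 1 − P(|Z₁| < 1.96 and |Z₂| < 1.96) for two standard normal statistics with correlation ρ. At ρ = 0 this is 1 − 0.95² = 9.75%.

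| ρ (assumed) | 0 | 0.3 | 0.5 | 0.7 | 0.9 |
|---|---|---|---|---|---|
| At least one false positive | 9.75% | 9.5% | 9.1% | 8.4% | 7.0% |

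The number of measures and their correlation are assumptions.

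**The case against.** The strongest reply is that CSHQ is plainly meant. It is the only measure the trial is powered on, one score range is given for it, and no separate instrument matches the second example. On that reading the error rate is 5% and the loose wording is minor. This is a fair reading and may be the intended one, but the text does not state it, and it still leaves the visit open.

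On power, 3 months describes where the earlier study saw its effect; the protocol does not say that its own primary test falls there, and 26 per arm is right for d = 0.8 at any visit. That stands, and the calculation is not disputed. What is missing is any statement that -0.8 is expected at the visit where both arms are measured. An effect soon after treatment could also be larger than 0.8, and covariate adjustment could raise power, so the table in step 3 shows a risk and does not forecast a shortfall.

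The regression sentence in the Analysis Plan names no visit, so a 3-month between-arm estimate is its natural reading but not an explicit one. The hypothesis, however, states that contrast outright, and it conflicts with the schedule however the Analysis Plan is read.

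Finally, parents' awareness of allocation applies to CSHQ too, so fixing the endpoint does not remove it. That is correct; fixing the endpoint only removes the freedom to choose among such ratings.

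**Conclusion.** The concern holds. The primary outcome is not tied to one score or one visit, and the protocol contradicts itself at 3 months: a between-group benefit is hypothesised there, but no control measurement is scheduled. The contradiction is the weightier part and needs no assumption to establish. An unseen statistical analysis plan would not cure it, because the conflict lies between statements within the protocol.

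The numerical consequences are conditional. Power is 81% if -0.8 carries over to post-intervention, falling to 42% at an assumed effect of 0.5. The false-positive rate is 5% if CSHQ alone is primary, and 7.0% to 9.8% if either of two measures could be claimed. The sample size arithmetic is sound. The sponsor should correct this, and do so before outcome data are examined.

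**What to change.** 1. Name one primary endpoint: CSHQ total score (range 33 to 99) at the post-intervention assessment, compared between arms at two-sided 5%. Remove the examples from the definition.
2. Make the sleep diary, any CSHQ part-scores and other parent-reported sleep measures secondary.
3. In the sample size section, state that -0.8 was observed at 3 months, that the CSHQ score it refers to is not named, and that it is assumed to hold for the total score at post-intervention.
4. Align the hypothesis, schedule and Analysis Plan: report 3-month values as descriptive within-group data, with no between-arm claim.

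The alternative is to measure the waitlist group at 3 months as well. That adds an assessment. It also requires the protocol to say when waitlist families receive the intervention: the Risk/Benefit section says all selected participants will, but not when.

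The recommended route costs wording and one stated assumption. No new data are needed, because CSHQ is already scheduled post-intervention in both arms. The downsides are that no other parent-reported measure can be claimed as primary, and that power falls below 80% if the post-intervention effect is smaller than 0.8.

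### The between-arm analysis regresses change scores and adjusts for baseline only when the groups differ; it should always condition on baseline, because severity-related loss would otherwise bias it and precision is wasted.

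*Protocol*

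**What the plan says.** Three statements in the protocol bear on this.

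- **Principle** (Analysis Plan): "Subsequent analysis will be conducted on an intention to treat basis". The analysis set is not defined further.
- **Estimator** (Analysis Plan): "changes between baseline and post-intervention as well as between baseline and follow-up at 3 months will be computed", and then "Mean differences in change at 95% confidence interval in outcomes between intervention and control arms will be estimated with regression models". The same sentence adds covariates, and the baseline score of each measure, on the condition that the groups differ. A preliminary descriptive comparison of the two groups at baseline comes first. No other between-arm estimator is described.
- **Loss** (Sample Size Determination and Power): "To allow for 15% loss to follow-up, we require 30 families in each group".

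**The concern.** A change score needs both a baseline and a later score. If nothing is done about missing scores, the regression runs on the families who stay.

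That is not harmful in itself. It becomes harmful when the families who stay in one arm differ at baseline from those in the other and the model does not hold baseline constant. Families with high baseline scores tend to fall back towards the mean whatever their arm. If one arm loses more of its severe families, its average change shrinks for reasons unrelated to treatment.

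Uneven loss is conceivable here. Only the intervention arm attends two sessions, keeps the treatment diary and applies strategies at home, and the comparator is a waiting list. The primary outcome is parent-reported child sleep, so the main efficacy estimate is exposed.

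The condition on baseline adjustment gives little protection. A comparison of all randomised families at baseline cannot show an imbalance that loss creates later, and a significance test on about 25 families per arm would seldom detect one of the size found below.

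**Working it through.** Effects are in SD units, with improvement counted as positive.

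**1. The plan's own figures.** Sample Size Determination and Power asks for 26 families per arm, for 80% power in a two-sided 5% test. The effect size comes from this statement: "A previous representative study found an effect size of -0.8 for CSHQ at 3 months follow-up". A two-sample t-test at d = 0.8 has power 0.791 with 25 per arm and 0.807 with 26, so 26 is reproduced. For loss, 26 × 1.15 = 29.9, which gives the stated 30 (26 / 0.85 = 30.6 would give 31). At 15% loss, 60 × 0.15 = 9 families have no outcome and 51 remain, about 25.5 per arm. Power with 25 and 26 families is 0.80, so the sample size already covers the lost numbers. What remains is bias and avoidable variance.

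**2. Bias of the unadjusted change contrast.** Assumptions, none given in the documents:
- baseline and post scores each have SD 1 and correlation ρ of 0.3, 0.5 or 0.7;
- the true effect is 0.80;
- control loss is random;
- the log-odds of loss in the intervention arm rise by 1 per SD of baseline severity.

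Let δ be the amount by which mean baseline severity falls among retained intervention families. Expected change depends on baseline with slope ρ − 1, so

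change contrast = 0.80 − (1 − ρ) × δ.

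Integrating the assumed loss model gives δ = 0.133 at 15% loss and 0.141 at 16%.

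| ρ | 15% loss | 16% loss |
|---|---|---|
| 0.3 | 0.80 − 0.7 × 0.133 = 0.71 | 0.80 − 0.7 × 0.141 = 0.70 |
| 0.5 | 0.80 − 0.5 × 0.133 = 0.73 | 0.80 − 0.5 × 0.141 = 0.73 |
| 0.7 | 0.80 − 0.3 × 0.133 = 0.76 | 0.80 − 0.3 × 0.141 = 0.76 |

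Simulation with 400,000 families per arm and 15.5% loss gave 0.703, 0.732 and 0.759. If milder families are lost instead, the sign reverses: simulation gave 0.89, 0.87 and 0.84.

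**3. What removes the bias.** A regression on the same retained families, with every lost family still left out but baseline always in the model, returned 0.80 at all three correlations. So the cause is the missing baseline term, not the absence of the lost families. With one later score per family, a family with only a baseline score adds essentially nothing to the arm contrast.

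**4. Whether the stated condition helps.** The protocol does not say how a group difference is judged. Read as a 5% test at baseline (an assumption), the conditional rule gave 0.71, 0.73 and 0.76 in simulation. A retained-family imbalance of about 0.13 SD would be significant only about 7 to 8% of the time with some 25 families per arm.

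**5. Precision.** Residual variance is 2(1 − ρ) for change and 1 − ρ² after conditioning on baseline.

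| ρ | Change | Conditioned on baseline | SE ratio |
|---|---|---|---|
| 0.3 | 1.4 | 0.91 | √(0.91/1.4) = 0.81 |
| 0.5 | 1.0 | 0.75 | √(0.75/1.0) = 0.87 |
| 0.7 | 0.6 | 0.51 | √(0.51/0.6) = 0.92 |

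Against the conditional rule, which adjusts occasionally, the simulated gain was a 5 to 14% smaller standard error.

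**6. What conditioning does not repair.** Suppose the 15% lost from the intervention arm gained nothing, for reasons unrelated to baseline. The effect over all randomised families is then 0.85 × 0.80 = 0.68, while the retained families show 0.80, an overstatement of 18% (0.80 / 0.68 = 1.18). A baseline-conditioned model also returns 0.80 here.

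**The case against.** A reader might go further and infer that the plan contradicts its own intention-to-treat promise and drops every family without a later score. The document does not support that. It nowhere says that such families are excluded, that only completers are analysed, or that scores are not imputed before changes are computed. Intention to treat is also used to mean analysis in the arm assigned, which the text allows. Missing-data handling is commonly left to a separate statistical analysis plan, so its absence is no finding.

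Three further objections have force.

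- **Baseline adjustment is already listed.** It is, and where applied it gives the right answer in step 3. What fails is the condition attached to it.
- **The loss mechanism is assumed.** The documents give no mechanism and no baseline-post correlation, and the direction of bias depends on who leaves. This limits the size of the claim. It does not touch the precision gain, which needs no assumption about loss.
- **The 15% is an allowance.** It follows an effect quoted at 3 months. The post-intervention visit comes one week after the follow-up call, so loss by then may be smaller, and the bias with it.

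**Conclusion.** The point holds in a limited form. The stated between-arm estimator conditions on baseline only if the groups differ. Unless an unstated missing-data method is added, it uses only families with a later score.

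Under severity-related loss confined to the intervention arm, at about the budgeted rate, it understates a true 0.80 by roughly 0.04 to 0.10 SD. Opposite selection would overstate it by about as much. If loss is unrelated to baseline there is no such bias, but the estimate is still less precise than it need be whenever the baseline-post correlation lies in the range shown.

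The size rests on the assumed loss model, equal SDs and correlations of 0.3 to 0.7. The charge of a broken intention-to-treat promise is not made out.

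**What to change.** In the Analysis Plan, remove the condition that ties baseline-score adjustment to a group difference. State that the arm difference at post-intervention is always conditioned on the baseline score of the measure concerned, with families analysed in the arm to which they were randomised. ANCOVA is enough; a linear mixed model with a common baseline mean is equivalent here.

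This relies on data being missing at random. To cover loss through unobserved lack of benefit, one CSHQ sensitivity analysis may be added in which lost intervention families take the control-arm mean change. Under the assumptions of step 6 it would give 0.68.

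The wording covers post-intervention only. The measurement schedule under Other Information assigns the 3-month assessment to the intervention group alone, so a between-arm change to 3 months must be reconciled with that schedule separately.

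The cost is a change of wording and a little programming, with no change to visits or sample size. The downsides are the missing-at-random assumption and a sensitivity estimate that may be less favourable.
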